# 9.3 Specimen Banking

Subject samples collected for this study will be retained at the department of pathology and at the lab of [name] (NC7. 208). Specimen may be shipped to companies or outside institutions to perform specialized assays, a non-extensive list of which is provided above. Specimen will be shipped de-identified. Specimens will be stored indefinitely or until they are used up. If future use is denied or withdrawn by the subject, best efforts will be made to stop any additional studies and to destroy the specimens.

[name] will be responsible for reviewing and approving requests for clinical specimen from potential research collaborators outside of UTSW. Collaborators will be required to complete an agreement (a Material Transfer Agreement or recharge agreement) that states specimens will only be released for use in disclosed research. Any data obtained from the use of clinical specimen will be the property of UTSW for publication and any licensing agreement will be strictly adhered to.

The specimens, DNA, and their derivatives may have significant therapeutic or commercial value. The Informed Consent form contains this information and informs the subject that there is the potential for financial gain by UTSW, the investigator or a collaborating researcher or entity.

The following information obtained from the subject's medical record may be provided, among other, to research collaborators when specimens are made available:

- Diagnosis
- Collection time in relation to study treatment
- Clinical outcome if available
- Demographic data

# 10.0 QUALITY OF LIFE AND COST-EFFECTIVENESS

#### 10.1 Health-Related Quality of Life (HRQOL) Analysis

The study design is to prospectively analyze the HRQOL among patients with mRCC treated with SABR and HD-IL-2. While hypofractionation is hypothesized to yield greater tumor cell kill, it may also increase the normal tissue toxicity, in which case there may be a decrease in HRQOL. The primary normal tissue toxicities in patients receiving radiation depends on the location of the treatment. Prior studies have demonstrated that the most sensitive and clinically meaningful method for accurately capturing the normal tissue toxicities is via patients reported outcomes (PROs), such as HRQOL.

In this non-randomized trial, we plan to assess the FACT-G at specific time points to minimize patient burden: baseline (pretreatment), end of HD-IL-2 cycle 2 treatment, and at subsequent follow ups (See Appendix). In order to analyze the QOL, we plan to use a brief, validated instrument that is user friendly and has clinical relevance [111]. FACT-G is a measure that sums the functional well being (FWB), physical well being (PWB), the social/family well-being (S/FWB), and emotional well being(EMB). FKSI adds to the FACT-G (27 items) by including 15 items specific to prostate cancer patients. The FACT-G has been validated as well and

used in other studies evaluating treatment options for patients with mRCC [106]. It takes about 5-10 minutes to complete and has been written at the 6th grade level. FACT has been translated into 26 languages and is available free of charge to institutions with the completion of an agreement to share data, accessible at http://www.facit.org/translation/licensure.aspx.

In a HRQOL study focused on patient with mRCC a symptoms subscale questionnaire was developed and will also be administed in this study. It is 15 questions and should take less than 5 minutes to complete. This form focuses on symptoms frequently experienced by renal cell carcinoma patients and has been used in several recent mRCC studies [112]

In addition, the EQ-5D. EQ-5D is a standardized instrument for use as a measure of health outcome. Applicable to a wide range of health conditions and treatments, it provides a simple descriptive profile and a single index value for health status. The US version of the EQ-5D will be used, to enable mapping of general HR-QoL scores from EQ-5D scores into health state utility scores (ranging from 0 to 1) for the US population. These utility scores are needed for cost-utility analysis (estimates of costs per "quality adjusted" life-year gained) [113, 114].

HRQoL of patients with mRCC is unfortunately not well described in the literature for either treatment modalities in this study or other standard of care treatments as well. A review of patient reported outcomes and health-related quality of life studies in the modern era of metastatic renal cell carcinoma is available highlighting the great need to assess patient reported outcomes in this patient population [84].

There is little reported on the effect on HRQOL for patients treated with HD-IL-2, No specific data has been published other than in abstract form and this data showed stable QoL between several IL-2 dosing patterns [81] However, there are several detailed reports evaluating quality of life for sunitinib, sorafanib. temsirolimus, everolimus, pazopanib [115]. Thus, we propose utilizing the FACT-G, FKSI, and EQ-5D in the patients enrolled on this study for descriptive purposes given the lack of HR-QoL data for either IL-2, HD-IL-2, or SABR in this patient population [116].

Additionally, in order to calculate the indirect costs associated with hypofractionated radiation treatment, a single administration of a short economic questionnaire will take place at the end of radiation treatment or first available follow up or whichever occurs first. This questionnaire which has been adapted for administration in the United States has been used in economic assessments in rural Canadian cancer health service research [117].

#### 10.2 Cost-Effectiveness Analysis (CEA)

For the primary CEA analysis, we will estimate cost accumulated within 1 years after enrollment. A larger limit is possible if we have a reasonable number of people surviving at that time.

Since patients are enrolled into the study over time and some patients are still alive at the end of the study, their survival time and costs are censored. Due to the presence censoring, we cannot use a simple average of the patients' total costs, a simple average of the patients' costs for those with complete cost information, or a Kaplan-Meier estimator on censored costs, since these all produce biased estimators of the mean costs[113]. Instead, we will use the inverse-probability weighting method to calculate average costs.[114, 118] The assumption used in this method is that censoring is independent of the survival time, or cost collection process, which is often satisfied in well-conducted clinical trials. If the new treatment can both extend patients' survival time (or quality-adjusted survival time), and save costs at the same time, the new treatment will be preferred to the current standard treatment under any willingness to pay threshold.

However, if the new treatment extends survival time but costs more, cost-effectiveness analysis provides an estimate of the incremental cost of greater incremental effectiveness. For traditional cost-effectiveness analysis, treatment effectiveness is measured simply as survival time. The incremental cost-effectiveness ratio indicates the additional cost required to attain one additional year of survival. For cost-utility analysis, treatment effectiveness is measured as quality-adjusted survival time (which accounts for the impact of treatment on both mortality and morbidity, including any differences in adverse affects of treatment affecting HR-QoL). For cost-utility analysis, the incremental cost-effectiveness ratio indicates the additional cost required to attain one additional year of quality adjusted survival.

#### 10.2.1 Projection Model and Sensitivity Analysis

If the new treatment is implemented in usual practice, some of its potential benefits to patients may extend beyond the time horizon of the clinical trial. We will explore the potential to use results from the clinical trial based cost-effectiveness analysis, augmented with information from secondary sources, to develop a model to project costs and effectiveness beyond the time horizon included in the clinical trial. Any such model projections would be subjected to probabilistic sensitivity analysis, to assess the impact of parameter uncertainty on estimated cost effectiveness results. This is typically done via Markov Modeling with probabilistic sensitivity analysis.

#### 10.3 Quality adjusted survival time:

The quality-adjusted survival time estimates need to account for the presence of censoring. Due to the induced informative censoring problem, the ordinary survival method (e.g., Kaplan-Meier estimator) cannot be applied in this case [114, 118, 119]. Accordingly, we will use the inverse-probability weighted method of Zhao and Tsiatis to carry out the survival time analysis [114, 118]. To estimate quality adjusted survival time, data from EQ-5D will first be translated into utility measures. These measures are obtained at discrete time points, so they will be interpolated into the time intervals between the visits. The quality-adjusted survival time is just an integration of the utility measures over a patient's survival time, or until the time limit similar as the cost calculation, whichever occurs earlier.

# 11.0 STATISTICAL CONSIDERATIONS

# 11.1 Study Design/Study Endpoints

This is an open label phase II non-randomized single arm prospective clinical trial. The primary end point is RR, while the secondary end points include improvement in OS, PFS, immunologic response, toxicity and quality of life (Please see endpoint details in section 2 and 6).

#### 11.2 Sample Size and Accrual

The previous studies show that the maximum RR for mRCC patients treated with HD IL-2 is 23% [35]. We expect a >60% improvement in this rate leading to a 36.8% RR for mRCC patients when treated with SABR and IL2. The calculation of the sample size is based on the RR and Simon's optimal two-stage design will be used with  $(\alpha,\beta)=(0.20, 0.20)$  [120]. The RR of 23% is set as the lowest desirable rate and 36.8% is the rate we are targeting. We chose type I error of 0.20 and type II error of 0.20. That is, if the true response rate is less than 23%, the probability of wrongly accepting the treatment for further study is 20%, and if the true response rate exceeds 36.8%, the probability of wrongly rejecting it for further study is 20%. According to the optimal two-stage design, a maximum of 33 patients will be needed. In the first stage, 17 patients will be evaluated. If 3 or fewer responses are observed, then the trial will be terminated for futility. Otherwise an additional 16 patients (second stage) will enter the trial. Finally, if more than 9 responses are observed among 33 patients, then the regimen

(SABR+IL-2) may be considered as the experimental arm of a Phase III trial. The average sample size for this phase II trial is 26.2 patients, and the probability of early termination is 0.43 for a drug with response probability of 23%.

# 11.3 Data Analyses Plans

This is a single-arm Phase II trial of SABR and HD IL-2 for mRCC patients. PFS and OS, will be estimated using the Kaplan-Meier approach along with the 95% confidence interval. Exact binomial method will be used to calculate the response rate, toxicity and the corresponding 95% confidence interval. One-sample log-rank test [121] will be used to test if the survival endpoints such as OS or PFS are significantly different from those in the historical control reported in McDermott et. al [35].

Generalized estimating equation (GEE) analysis will be conducted to test if the median number of spots in Elispot of the PBMC collected from patients are significantly different over time (before starting of treatment and after SBRT, at 8 weeks and six months). T-Cell proliferation SI will also be evaluated in the same manner.

HRQol, CEA and quality adjusted survival time analysis is described in Section 10.

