Therefore, we propose a single-arm, open-label, phase II trial of HD IL-2 and SABR to multiple sites of bulky disease. The toxicities of HD IL-2 are significant and well known. Given the multiple studies demonstrating excellent safety profile of SABR, including our own departmental experience, there are limited concerns for additional toxicity when they are administered sequentially [2-4]. In fact, a phase I trial of HD IL-2 and SBRT in melanoma and RCC patients has proven the safety and feasibility of this regimen [61]. This small study showed a CT evidence of PR in 3 out of 5 (60%) and a PET CR in 1 out of 5 (20%) mRCC patients treated with HD IL-2 immediately after SBRT. Given the short duration of their median follow up (480 days) it remains to be seen how many mRCC patients remain disease free in the long run.

The primary endpoint of this study is to measure improvement in response rate (RR) and compare it to the historically reported data. As reported in three randomized trials, the RR for HD IL-2 in mRCC is 20%-23% (see below). A significant improvement on the historically reported RR would justify seeking a phase III trial to show the efficacy of this regimen in improving overall survival. The secondary objectives of this trial will measure progression-free survival (PFS), overall survival (OS), time to progression (TTP), duration of treatment response and tumor-specific immune response, each of which also has the potential to be used as justification for a phase III trial. In addition, the exploratory objectives will include correlation of the immune response to clinical outcome, exploration of immunologic biomarkers to predict response, improvement in health-related quality of life (HR-QoL) and cost effectiveness analysis. Given the high cost of HD IL-2, requiring multiple ICU admissions for patients, it will be worthwhile to explore the cost effectiveness of adding SABR in improving the outcome of HD IL-2 treatment alone and perhaps in decreasing the number of treatments required to achieve the same or improved RR, and then analyzing the improvement in HR-QoL, the quality-adjusted survival and cost effectiveness of this regimen.

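### Section 11.3 gives the response rate an unadjusted exact binomial estimate and 95% CI although it comes from a two-stage design with a futility stop; the effect is modest and falls mainly on no-go results.

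*Combined protocol and SAP*

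**What the plan says.** Section 11.2 bases the sample size on response rate: "The calculation of the sample size is based on the RR and Simon's optimal two-stage design will be used with" both error rates at 0.20. The hypotheses are explicit: "The RR of 23% is set as the lowest desirable rate and 36.8% is the rate we are targeting". The stage-1 rule reads "In the first stage, 17 patients will be evaluated" and "If 3 or fewer responses are observed, then the trial will be terminated for futility". Otherwise 16 more patients enter, and the regimen may be considered for phase III "if more than 9 responses are observed among 33 patients". The section reports an average sample size of 26.2 and an early-termination probability of 0.43 at 23%.

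Section 11.3 then gives one sentence on estimating the response rate: "Exact binomial method will be used to calculate the response rate, toxicity and the corresponding 95% confidence interval". Response and toxicity share the method, although only response has a stage-1 stopping rule. Neither section names a two-stage estimator, interval or p-value. Section 11.3 plans no test of response at all; its tests concern the survival endpoints and the immune assays.

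**The concern.** A response count that could have been cut off at 17 patients is not one fixed binomial sample. Runs of poor early results are frozen at 17 patients with no chance to recover, so the plain proportion is too low on average. An exact binomial interval computed as if 17 or 33 had been fixed in advance does not carry its nominal error in each tail.

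Response rate is the primary endpoint, and its estimate and limits will be quoted when a next trial is planned. If the method is not named beforehand, the choice between a plain and a two-stage analysis will be made with the data in view.

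**Working it through.** **Inputs (Section 11.2).** n1 = 17, stop at r1 = 3 or fewer; n2 = 16, N = 33; go at 10 or more; p0 = 0.23, p1 = 0.368; one-sided alpha = 0.20, beta = 0.20. From Section 11.3: exact binomial estimate and 95% CI, read as the sample proportion with Clopper-Pearson limits.

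**Step 1: reproduce the design.** With X1 ~ Bin(17, p) and X2 ~ Bin(16, p):
- P(stop | 0.23) = P(X1 ≤ 3) = 0.427 (plan: 0.43).
- Expected N = 17 + 16 × (1 − 0.427) = 26.2 (plan: 26.2).
- Attained alpha = P(X1 ≥ 4 and X1 + X2 ≥ 10 | 0.23) = 0.197; power at 0.368 = 0.805.

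A search over designs returns 3/17, 9/33 as the optimal one, so Section 11.2 is correct.

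**Step 2: bias of the plain proportion.** E[estimate] = Σ over x ≤ 3 of (x/17)·P(X1 = x) + Σ over s ≥ 4 of (s/33)·P(X1 ≥ 4, X1 + X2 = s).
- True 23%: 21.04%, bias −1.96 points (about the maximum).
- True 30%: 28.51%, bias −1.49.
- True 36.8%: 35.99%, bias −0.81.

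**Step 3: error of the interval under the real design.** Add the probabilities of all outcomes whose Clopper-Pearson limit misses the truth.
- At 36.8%, the upper limit is too low after 0, 1 or 2 of 17 and after 4, 5 or 6 of 33; total 2.83%. The three stage-1 outcomes contribute 2.33%, so the excess over the nominal 2.5% comes from the 4–6/33 results.
- The worst point is near 43.5%: upper miss 3.55%, lower miss 1.58%, so coverage = 100 − 3.55 − 1.58 = 94.87%. That is the minimum found.
- Coverage is 97.8% at 23%, 96.1% at 30% and 96.0% at 36.8%. The lower tail never exceeds 2.5%.

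**Step 4: two-stage analysis, result by result.** After a stage-1 stop the UMVUE is x/17. After stage 2 with s responses it is Σ C(16, x−1)·C(16, s−x) ÷ Σ C(17, x)·C(16, s−x), summing over stage-1 counts x ≥ 4 that are compatible with s. For s = 4 only x = 4 is possible: 560/2380 = 4/17 = 23.5%. The two-stage CI inverts tail probabilities with stage-1 stops ranked below all stage-2 results, then by count; the UMVUE gives the same order.

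| Result | Plain rate | Exact binomial 95% CI | UMVUE | Two-stage 95% CI |
|---|---|---|---|---|
| 3/17 | 17.6% | 3.8–43.4% | 17.6% | 3.8–43.4% |
| 4/33 | 12.1% | 3.4–28.2% | 23.5% | 6.8–43.4% |
| 5/33 | 15.2% | 5.1–31.9% | 24.4% | 7.4–43.4% |
| 6/33 | 18.2% | 7.0–35.5% | 25.4% | 8.5–43.6% |
| 8/33 | 24.2% | 11.1–42.3% | 28.1% | 11.7–45.1% |
| 9/33 | 27.3% | 13.3–45.5% | 29.9% | 13.7–46.9% |
| 10/33 | 30.3% | 15.6–48.7% | 31.9% | 15.8–49.3% |
| 12/33 | 36.4% | 20.4–54.9% | 36.9% | 20.5–55.0% |
| 14/33 | 42.4% | 25.5–60.8% | 42.5% | 25.5–60.8% |

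Two features stand out. The plain upper limit drops from 43.4% at 3/17 to 28.2% at 4/33, although the second trial did better at stage 1. At 5/33 and 6/33 the plain limits exclude the 36.8% target; the two-stage limits do not.

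**Step 5: how often this matters.** At a true 23%, P(4–9 of 33) = 1 − 0.427 − 0.197 = 0.376. At 30% it is about 27%. At the 36.8% target, 4–8 of 33 has only about 5% probability.

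**Step 6: p-value at the go boundary, if one is reported.** For 10/33 against 23%: fixed-sample exact 0.211; two-stage 0.197.

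**The case against.** The strongest reply is that the decision is safe and the numbers hardly move where a go is declared. This stands. Section 11.2 decides on a count with correct error rates, and nothing in 11.3 overrides it. From 10/33 upwards the two estimates differ by 1.6 points or less. The bias is downward, so it does not flatter the regimen, and total coverage holds at about 95% or more. It is also true that 11.3 does not say one-stage; that is the natural reading of its wording, not a statement in it.

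Three stronger readings are tempting but not supported.
- A reader might infer that the planned analysis contradicts the go rule, because the fixed-sample p-value at 10/33 is 0.211, above 0.20. Section 11.3 plans no p-value for response, so there is nothing to contradict.
- A reader might count it against 11.3 that a go at 10 to 13 of 33 comes with a 95% CI that includes 23%. The two-stage CI includes it as well; both first exclude 23% at 14/33. The cause is a 95% interval set beside an alpha of 0.20.
- The rationale in Section 1.4.1 says "A significant improvement on the historically reported RR would justify seeking a phase III trial", which might suggest a conventional significance level. That is background text, and 11.2 openly states "We chose type I error of 0.20 and type II error of 0.20".

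A two-stage estimate also has a cost. It is unbiased only when early stops are averaged in. Among trials that reach a go, the plain rate is already too high and the UMVUE is slightly higher: on average 34.6% versus 33.5% at a true 23%, and 40.0% versus 39.5% at 36.8%. At 23% its root mean squared error is 9.3 versus 8.8 points, although it is smaller than that of the plain rate at 30%, 36.8% and 43.5%.

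**Conclusion.** The point holds as a matter of estimation and reporting for the primary endpoint. The unadjusted method understates the response rate by up to about 2 points on average, lets the upper-tail error reach 3.55% instead of 2.5%, and gives upper limits that are out of order between 3/17 and 4/33. The practical effect is on no-go results of 4 to 9 of 33: the plain rate is 2.6 points below the UMVUE at 9/33 (29.9 − 27.3) and 3.9 below at 8/33 (28.1 − 24.2), and at 5/33 and 6/33 its upper limit rules out the target when a two-stage limit would not. The documents do not support any claim that the go decision is mis-sized or contradicted.

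This rests on reading the exact binomial wording as the sample proportion with Clopper-Pearson limits, and on the 3/17, 9/33 design in 11.2 being followed exactly. The Study Summary lists a different average and maximum (33 and 38); the figures here use 11.2.

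**What to change.** In Section 11.3:
- Report the UMVUE of the response rate and a 95% CI from the two-stage sample space, naming the ordering, with the plain proportion beside them.
- State that the go decision rests on the count rule in 11.2, at one-sided alpha 0.20.
- If a p-value against 23% is reported, use the two-stage one (0.197 at 10/33).
- Keep the exact binomial method for toxicity as a separate sentence.

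The cost is a few lines of plan text and a short exact calculation; sample size and conduct do not change. Because the UMVUE is a little higher than the plain rate after a go and slightly more variable around the truth at 23%, both figures should be shown.

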## 2.2 Secondary Objectives

- **2.2.1** To evaluate the overall survival (OS), which is defined as the time between date of registration and the date of death due to any cause. In analyzing the OS, it is important to take into account the MSKCC prognostic criteria defined by Motzer et. al. mRCC patients and compare the outcome in the appropriate risk categories [90].
- **2.2.2** To evaluate progression free survival (PFS), which is defined as the time between date of registration and the first date of documented disease progression or date of death due to any cause.
- **2.2.3** To evaluate time to progression (TTP), which is defined as time between date of registration and date of documented progression.
- **2.2.4** To evaluate the local control rate of irradiated lesions.
- **2.2.5** To evaluate median response duration, which is defined as the time between the date a response (CR or PR) was first seen until date of progression.
- **2.2.6** To measure treatment-related tumor-specific immune response.
- **2.2.7** To evaluate the tolerability and toxicity of this regiment as measured according to CTCAE v4.0.
- **2.2.8** To measure the improvement in health-related quality of life (HRQoL).

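### The one-sample log-rank test for OS and PFS takes one historical curve as error-free, so its p-values are too small; for OS, section 11.3 also omits the MSKCC comparison that 2.2.1 asks for, leaving a bias of unknown direction

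*Combined protocol and SAP*

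**What the plan says.** Section 11.3 plans Kaplan-Meier estimates of PFS and OS with 95% confidence intervals. It then adds a formal comparison: "One-sample log-rank test [121] will be used to test if the survival endpoints such as OS or PFS are significantly different". The comparator is a single published source ("significantly different from those in the historical control reported in" reference 35, a randomised phase III trial of high-dose IL-2). The section gives no alpha, sidedness, event count or power for this test. It mentions neither uncertainty in the reference curve nor prognostic risk groups.

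Objective 2.2.1 says more about OS: "In analyzing the OS, it is important to take into account the MSKCC prognostic criteria", and the analysis should "compare the outcome in the appropriate risk categories". Objective 2.2.2, on PFS, has no such statement.

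The only error rates in the statistical section belong to the response rate (RR) in 11.2: "We chose type I error of 0.20 and type II error of 0.20". The Clinical Rationale in section 1.4 says that each secondary objective, OS and PFS among them, could serve to justify a phase III trial.

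**The concern.** A one-sample log-rank test compares observed events with those expected under a reference hazard treated as fixed. That suits a population life table. Here the reference comes from one trial arm, whose sampling error may be comparable in size to this trial's own. If that error is left out, the variance is too small and the test rejects too often in both directions.

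The second gap concerns OS only. Section 2.2.1 asks for outcomes to be compared within MSKCC categories, yet 11.3, where the OS analysis is specified, compares the whole cohort with one unadjusted curve. If the risk mix differs from that of the historical arm, the difference in mix appears as a treatment difference.

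At stake is a claim that survival differs from history, made from at most 33 patients (11.2) and available as an argument for phase III.

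**Working it through.** **Plan's own figures.** The only calculated design is the Simon two-stage design for RR in 11.2: "The RR of 23% is set as the lowest desirable rate and 36.8% is the rate we are targeting"; "According to the optimal two-stage design, a maximum of 33 patients will be needed". An exact binomial search returns the same optimal design: stop at 3 or fewer of 17, succeed at more than 9 of 33. Type I error is 0.1966, power 0.805 and probability of early termination 0.427. Expected size is 17 + (1 − 0.427) × 16 = 26.2. The plan's figures reproduce. There is no corresponding figure for the log-rank test.

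**Step 1: sampling error in the reference.** Let dE be trial events and dH historical events. The test uses a variance of about 1/dE on the log hazard-ratio scale. Counting the reference's error, it is about 1/dE + 1/dH, larger by the factor 1 + dE/dH. A nominal two-sided 0.05 test therefore has true size

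2 × [1 − Φ(1.96 / √(1 + dE/dH))].

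The inputs are dE = 33 (every patient at the 11.2 maximum has an event), 25 (assumed) and 17 (a stage 1 stop with all events observed). dH is assumed, because the documents do not give it. Example with dE = 33 and dH = 50: √1.66 = 1.288; 1.96/1.288 = 1.521; size 0.128.

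| Trial events | dH 50 | dH 75 | dH 95 | dH 150 | dH 300 |
|---|---|---|---|---|---|
| 17 | 0.090 | 0.077 | 0.071 | 0.063 | 0.057 |
| 25 | 0.110 | 0.090 | 0.081 | 0.070 | 0.060 |
| 33 | 0.128 | 0.102 | 0.091 | 0.076 | 0.063 |

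**Step 2: check by simulation.** Z = (O − E)/√E with 33 patients, exponential survival, an assumed median of 17 months, censoring between 48 and 72 months, no treatment effect and 20,000 replicates. With an exact reference, total rejection at ±1.96 is 5.4% (1.8% better, 3.5% worse). With a Nelson-Aalen reference estimated from 50, 100, 150 or 300 historical patients it is 13.5%, 9.8%, 8.0% and 6.5%. This agrees with the formula.

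**Step 3: risk mix.** To isolate this effect the reference is now exact. Assumptions: historical mix 20/60/20% good/intermediate/poor, relative hazards 0.5/1/2, no treatment effect.

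| Trial mix | Falsely better | Falsely worse |
|---|---|---|
| 20/60/20 (same) | 1.8% | 3.7% |
| 30/60/10 | 7.5% | 0.8% |
| 40/50/10 | 14.5% | 0.3% |
| 10/60/30 | 0.25% | 12.8% |

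A more favourable mix makes p-values for benefit too small, and a poorer mix makes them too large. The documents give neither mix, so no single row can be chosen.

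**Step 4: the variance factor with group-specific curves.** If expected events come from separate curves for each risk group, the factor becomes 1 + Σ(d_g²/H_g)/Σd_g, with d_g trial and H_g historical events in group g. Illustration: 33 trial events split 40/50/10% (13.2, 16.5, 3.3) and 100 historical events split 25/50/25%. The terms are 174.24/25 + 272.25/50 + 10.89/25 = 6.97 + 5.45 + 0.44 = 12.85, and 12.85/33 = 0.39, so the factor is 1.39. The single-curve factor, 1 + 33/100 = 1.33, would under-correct.

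**The case against.** OS and PFS are secondary. The only formal rule for moving on is more than 9 responses in 33, and section 1.4 speaks only of potential use for phase III. Kaplan-Meier estimates with intervals are already planned. Section 11.1 sends the reader to section 2 for endpoint details, so the MSKCC requirement has not been withdrawn, and a one-sample log-rank test can use expected hazards specific to each patient's risk group. All of this stands and limits the weight of the point. The accurate criticism is that 11.3 does not say how 2.2.1 will be carried out, not that the chosen test rules it out.

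The sizes also depend on assumed inputs. The upper figure, 0.128, needs 33 trial events and only 50 historical ones. With 25 and 95 the size is 0.081, still above 0.05. No finite historical arm removes the inflation entirely.

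Three stronger readings are tempting and are not supported:

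- *Both defects make benefit look too significant.* This holds for sampling error, which inflates rejection in both directions. It does not hold for risk mix, whose direction is unknown.
- *Eligibility guarantees a better-risk cohort.* ECOG 0–1 and the exclusion of life expectancy under 6 months (3.1, 3.2) might suggest so. But prior systemic therapy and treated brain metastases are allowed, the historical trial's eligibility is not in the documents, and 7.2.1 lists abnormal stress or pulmonary tests as contraindications to HD IL-2, so a historical HD IL-2 arm may have been similarly fit.
- *The plan contradicts itself on PFS.* Section 2.2.1 covers OS only. The same confounding could affect PFS, but no instruction is left undone there.

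**Conclusion.** The point holds, with moderate weight. Followed as written, the OS and PFS tests reject too often. At an assumed two-sided 0.05, true size is about 0.06 to 0.13 for 25 to 33 trial events and 50 to 300 historical events. This rests on a large-sample approximation confirmed by simulation, and on assumed event counts. The historical arm's actual number of events would replace the range with a single value for each trial event count.

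Separately, 11.3 does not implement the OS risk-category comparison in 2.2.1. The resulting bias could go either way. The illustrative 7 to 15% falsely better and 13% falsely worse depend wholly on the assumed mixes and hazards, so they show scale and are not predictions for this trial.

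A reader might infer that the trial's go decision is compromised. It is not: that decision rests on RR, and its design figures reproduce.

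**What to change.** Amend 11.3 as follows.

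1. For any OS or PFS test that is kept, allow for sampling error in the reference. With a single historical curve, multiply the variance by (1 + trial events/historical events). With group-specific curves, use 1 + Σ(d_g²/H_g)/Σd_g. Alternatively, apply a two-sample log-rank test to reconstructed historical data.
2. For OS, compute expected events from MSKCC-group-specific historical curves where these are published. Where they are not, report OS by MSKCC group beside the historical figures and label the historical comparison descriptive. Groups will be small (10% of 33 is about 3 patients), so group displays will be imprecise.
3. State alpha and sidedness. The present wording suggests a two-sided question but does not say so.

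The cost is wording in 11.3, some reconstruction of published curves, and less favourable p-values. No extra patients or visits are needed, and 2.2.1 already presupposes baseline MSKCC classification. The RR design and its decision rule do not change.
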